#### Primary outcome analysis

We will estimate the Intention-to-Treat (ITT) effect by estimating the following equation for young person i will be of the form:

$$Y_{i1} = \beta_0 + \beta_1 D_i + \beta_2 X_i + \beta_3 Y_{i0} + strata fixed effects + u_i$$

where  $Y_{i1}$  is the primary outcome of interest, which is an indicator that takes the value 1 if the young person scores in the high to very high conduct problems range and 0 otherwise, and  $Y_{i0}$  is the baseline value for that same outcome,  $D_i$  is an indicator for treatment assignment,  $X_i$  are any baseline characteristics of the young person and/or their team for which we find statistically significant imbalances between treated and control groups, and  $u_i$ is an error term. Standard errors will be clustered at the Local Authority level, following Chaisemartin and Ramirez-Cuellar (2022).

#### Secondary outcome analysis

Analysis of secondary outcomes will follow the same approach as for primary outcomes described above. To account for multiple hypothesis testing given the large number of secondary outcomes, we will calculate p-values using the step-down procedure of Romano and Wolf [2016]. The Romano-Wolf correction (asymptotically) controls the familywise error rate (FWER), that is, the probability of rejecting at least one true null hypothesis in a family of hypotheses under test. This correction is considerably more powerful than earlier multiple testing procedures such as the Bonferroni and Holm corrections, given that it takes into account the dependence structure of the test statistics by resampling from the original data. To implement it, we will use Stata's rwolf2 command, report unadjusted and adjusted *p*-values, and determine statistical significance of the results based on adjusted *p*-values below 0.05.

The estimating equation for ITT impacts for young period i will be of the form:

$$Y_{i1} = \beta_0 + \beta_1 D_i + \beta_2 X_i + \beta_3 Y_{i0} + strata \ fixed \ effects + u_i$$

where, as before,  $Y_{i1}$  is the secondary outcome of interest, and  $Y_{i0}$  is the baseline value for that same outcome (if any),  $D_i$  is an indicator for treatment assignment,  $X_i$  are any baseline characteristics of the young person for which we find statistically significant imbalances between treated and control groups, and  $u_i$  is an error term.

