# 2. Is there a difference in offending behaviour between young people allocated to work with a team of practitioner trained in Your Choice in comparison to young people allocated to work with a team of practitioner delivering BAU support?

The outcome of interest is whether participants are ever arrested in the first 16 months after recruitment, as recorded in the PCN database. This is a key secondary outcome given that it directly relates to and informs on Your Choice's goal of reducing violence among young people at most risk. However, the low frequency of criminal activity will raise challenges in detecting impacts on this variable, and the time lag to obtaining crime data will necessarily delay the analysis. For these reasons, we consider the study of impacts on crime activity to be exploratory.

Two intermediate outcomes will also be studied: the self-assessed and practitioner-assessed level of risk, measured at endline as part of the young person and practitioner survey taken in week 20 after recruitment. These will provide and earlier indication of effects on self and practitioners' perceptions of likelihood of engaging in risky behaviour.

The null hypothesis we will be testing are: (i) that there is no difference in arrest probabilities between young people allocated to Your Choice and young people allocated to business as usual and (ii) that there is no difference in the self and practitioner assessments of the young person's likelihood to engage in risky behaviour, between young people allocated to Your Choice and young people allocated to business as usual.

- **3.** What are the mechanisms through which Your Choice works? Specifically, in comparison to young people allocated to BAU support, do young people allocated to work with a team of practitioners trained in Your Choice:
  - Gain higher wellbeing and emotional self-regulation? These outcomes will be measured as part of the endline young person survey completed in week 20 after recruitment, using the Warwick-Edinburgh Mental Wellbeing Scale, the internalising subscales of the SDQ, and the Self-regulation subscale from the Trait Emotional Intelligence Questionnaire Adolescent Short Form (TEIQUE-ASF).
  - Have stronger relationships with their practitioners, with their family and other sources of social support? The outcome of interest will be the Social Connectedness Scale – Revised (SCS-R), included in the endline young person questionnaire (taken 20 weeks after recruitment).

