#### **Data**

For completeness and clarity it is worth briefly overviewing the data that will be available and the timing of data collection. More details can be found in the pilot report, with a copy of all questionnaires and of the session form available in Annex E of that report.

LA Workbook: Spreadsheet to be filled out by the SPOC/Data Lead of the Local Authority to provide background information about the young person, as well as a log of training dates for practitioners involved in the study and a log of clinical supervision sessions. The background information about the young person includes: date of birth, gender, ethnicity, SEN status, reason for referral into the service and any other services the young person is involved with. The workbook also includes a tab to list some basic demographic information (ethnicity, gender, age) about the young people who were approached to enter the study but who did not consent to and provides an option to explain the reason (if known) for non-consent.

Baseline young person questionnaire: The baseline young people survey is administered shortly after recruitment, in week 1, during a session with the assigned practitioner. It includes the Strengths and Difficulties Questionnaire (SDQ), a scale developed by the evaluation and project team about the young person's safety (young person Checkpoint), the Social Connectedness Scale — Revised (SCS-R), the Pro-Social IDentity Scale (PIDS) and a question about the young person's main activity at the time of the survey.

Baseline practitioner questionnaire: The baseline practitioner survey is completed shortly after recruitment, in week 1. It asks the young person's practitioner to report their risk rating of the young person, as well as their perception of the young person's safety using the practitioner version of Checkpoint.

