Endline young person questionnaire: The endline young people survey is administered at the end of Your Choice period, in week 20 after recruitment, during a session with the assigned practitioner. It includes the same content as the baseline young person questionnaire, plus the following scales: The Short Warwick–Edinburgh Mental Well-being Scale (SWEMWBS), the Trait Emotional Intelligence Questionnaire – Adolescent Short Form (TEIQUE-ASF) – Self regulation subscale, and the Pro-Social IDentity Scale (PIDS). The latter were excluded from the baseline survey to keep it as short as possible while focusing on the most relevant measures, and also because these scales are most interesting as outcomes rather than as conditioning variables given the rich data we already collect at baseline. The endline questionnaire also asks the young person some questions about their experience working with their practitioner: it asks whether they would recommend it to someone else, it provides a free text box for any additional comments, and it asks a series of 7 questions about the practitioners' approach and practices to working with the young person. These approaches/practices were selected to be those most characteristic of the practices embedded in the Your Choice training.

Endline practitioner questionnaire: The endline practitioner survey is completed at the end of Your Choice period, in week 20 after recruitment. It includes the practitioner version of Checkpoint, as well as a series of 7 questions about the practitioners' approach and practices to working with the young person. These approaches/practices are the same as the ones asked to the young person in the endline questionnaire and were selected to be those most characteristic of the practices embedded in the Your Choice training.

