Step 6. Investigation of potential mechanisms through which Your Choice affects externalising behaviour, arrests or risk assessment. We will regress each of the other secondary outcomes measured at endline (week 20 after recruitment) on a treatment indicator, the baseline value of that variable where available, other observed characteristics where imbalances at baseline were found (steps 1 and 2), and local Authority fixed effects. This will provide suggestive evidence on potential mechanisms underlying identified responses in externalising difficulties and criminal behaviour and risk, as detailed in the Logic Model. Effects will be shown in standard deviation units. Standard errors will be clustered at the local authority level and we will show the 95% confidence interval for the estimated effect. This analysis addresses research question 3. We will not run a fully fleshed mediation analysis because we do not have exogenous variation to independently vary the mediators.

Step 8. Heterogeneity analysis of the impact of Your Choice on the primary outcome (conduct problems) and criminal activity (possibility of arrest). This will be carried out by adding interaction terms between the treatment indicator and variables describing key demographic and contextual factors. Specifically, we will interact the treatment indicator with age, gender, ethnicity, special education needs and practitioner risk assessments at baseline. This analysis will address research question 4.

15

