*Wellbeing*: The Short Warwick–Edinburgh Mental Well-being Scale (SWEMWBS). Part of the endline young person questionnaire, which is administered at some point between weeks 14 and 20 after recruitment.

*Emotional self-regulation*: Trait Emotional Intelligence Questionnaire – Adolescent Short Form (TEIQUE-ASF) – Self regulation subscale. Part of the endline young person questionnaire, administered at week 20 after recruitment.

Social connectedness: Social Connectedness Scale – Revised (SCS-R). Part of the endline young person questionnaire, administered at week 20 after recruitment.

Internalising behaviours: emotional difficulties and peer difficulties subscales of the SDQ measured at baseline and endline as part of the participant's surveys administered following recruitment and at week 20 after recruitment respectively.

*Hyperactivity*: hyperactivity subscale of the SDQ measured at baseline and endline as part of the participant's surveys administered following recruitment and at week 20 after recruitment respectively.

*Prosocial behaviours*: Strength and Difficulties prosocial behaviour subscale measured at baseline and endline as part of the participant's surveys administered following recruitment and at week 20 after recruitment respectively.

*Prosocial identity*: Pro-social Identity Scale (PIDS) measured at baseline and endline as part of the participant's surveys administered following

		recruitment and at week 20 after recruitment respectively.	
	variable	Conduct problems	
Baseline for primary outcome	measure (instrument, scale, source)	Indicator for scoring in the high or very high range of conduct problems scale from the Strengths and Difficulties Questionnaires.	
		Measured as part of the baseline participant's survey, administered in week 1 after recruitment, before the start of Your Choice.	
	variable	Social connectedness score, internalising behaviour, hyperactivity, prosocial behaviour and prosocial identity, self-reported and practitioner-reported perceptions of young person's safety.	
	measure (instrument, scale, source)	All measured as part of the baseline participant's survey, administered in week 1 after recruitment, before the start of Your Choice.	
Baseline for secondary		Social connectedness: The Social Connectedness Scale – Revised (SCS-R), survey of young person following consent before Your Choice starts (in some cases, some form of BAU work/support will have already been taking place).	

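### The main models for wellbeing (SWEMWBS) and emotional self-regulation (TEIQUE-ASF) have no pre-specified prognostic covariate, although related SDQ scores are collected at baseline

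*SAP*

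**What the plan says.** **Main model.** The SAP (Secondary outcome analysis) regresses each endline outcome on treatment, strata effects, Y_i0 and X_i. Y_i0 "is the baseline value for that same outcome (if any". The X_i "are any baseline characteristics of the young person for which we find statistically significant imbalances between treated and control groups". Protocol Analysis, Step 6, has the same rule: it adjusts for "the baseline value of that variable where available". Significance for secondary outcomes is judged on Romano-Wolf adjusted p-values.

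**No baseline for two outcomes.** In the SAP Design overview, SWEMWBS is "Part of the endline young person questionnaire, which is administered at some point between weeks 14 and 20 after recruitment", and TEIQUE-ASF is likewise placed at endline only. The list of secondary outcomes with a baseline measure begins "Social connectedness score, internalising behaviour, hyperactivity, prosocial behaviour and prosocial identity" and then adds perceived safety; neither scale is in it. The protocol (Data, endline young person questionnaire) gives two reasons. One is to keep the baseline survey short. The other is that "these scales are most interesting as outcomes rather than as conditioning variables given the rich data we already collect at baseline".

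**Related baseline data.** The SDQ is in the week-1 survey. Protocol research question 3 takes wellbeing and emotional self-regulation together, measured "using the Warwick-Edinburgh Mental Wellbeing Scale, the internalising subscales of the SDQ, and the Self-regulation subscale from the Trait Emotional Intelligence Questionnaire".

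**Secondary specifications.** SAP Robustness checks adds a simple model (treatment and strata effects only) and a post-double-selection LASSO that can pick covariates predictive of the outcome. The protocol's candidate covariates include baseline SDQ scores.

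**The concern.** The protocol leaves these two scales out of the baseline survey partly because other baseline data are rich, yet the main model does not call on those data for these outcomes. If no characteristic is significantly imbalanced, their main model reduces to treatment plus strata effects. That is the simple model the SAP lists as a robustness check, so for these outcomes the check would repeat the main analysis.

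Both outcomes are tied to the logic model in the protocol's Secondary outcomes section. A related baseline score, if it predicts the endline score, would narrow the intervals without new data collection. The expected analysed sample has also fallen from 1,272 to 1,094 in the SAP, so precision is scarcer than first planned.

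**Working it through.** **Inputs from the documents.** Protocol Table 6: MDE 0.16 SD for a continuous externalising score (SD 1, ICC 0.12, 30% attrition, strata effects, no lagged outcome), 80% power, two-sided 5%. Protocol Table 7: MDE 0.12 SD with a lagged score (variance 0.6, ICC 0.05). Protocol Table 5: 960 and 801 participants, total 1,761, including 83 pilot participants with endline data. SAP revision: 1,094 analysed, arms of 937 and 626 out of 1,563, ICC 0.09. No power or MDE is stated for SWEMWBS or TEIQUE-ASF.

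**Step 1: the nearest stated figures.** Analysed N = 1,678 × 0.7 + 83 = 1,257.6, and treated share p = 960/1,761 = 0.545. With LA effects removed, MDE = (critical value + power quantile) × √[variance × (1 − ICC) / (N p(1 − p))].
- No lagged score: 2.80 × √[0.88/(1,257.6 × 0.545 × 0.455)] = 0.149; with t on 28 df, 0.154. A simulation of the documents' data-generating process, on an assumed layout of 29 LAs and 133 teams, gave 77% power at 0.16 and 85% at 0.17. The stated 0.16 is consistent with these. An exact match cannot be tested, because the layout by LA is not published.
- Lagged score, variance 0.6, ICC 0.05: 0.120 (normal) or 0.124 (t). This fits the stated 0.12. Protocol Table 4 gives a residual SD of 0.5, a variance of 0.25, which would give about 0.08. Tables 4 and 7 disagree on this input.

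**Step 2: effect of a proxy covariate.** Let r be the within-LA correlation between the baseline SDQ covariates and the endline outcome. It is an assumption throughout. Residual variance is multiplied by (1 − r²), so:
- MDE = 0.16 × √(1 − r²)
- Power at 0.16 SD = Φ(2.80/√(1 − r²) − 1.96)
- Equivalent gain in participants = 1/(1 − r²) − 1
- If complete cases are used, the gain is cancelled once a fraction r² of participants lack the covariate, because (1 − r²)/(1 − m) = 1 at m = r².

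| r (assumed) | MDE from 0.16 | Power at 0.16 SD | Equivalent extra participants | MDE, revised sample (t, 28 df) | Missing baseline that cancels the gain |
|---|---|---|---|---|---|
| 0 | 0.160 | 80% | – | 0.171 | – |
| 0.2 | 0.157 | 82% | 4% | 0.167 | 4% |
| 0.3 | 0.153 | 84% | 10% | 0.163 | 9% |
| 0.4 | 0.147 | 86% | 19% | 0.157 | 16% |
| 0.5 | 0.139 | 90% | 33% | 0.148 | 25% |

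The revised-sample column uses N = 1,094, p = 937/1,563 and variance 0.91 × (1 − r²). All figures are before the Romano-Wolf adjustment.

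**Step 3: PIDS.** The protocol's description of the baseline young person questionnaire includes "the Pro-Social IDentity Scale (PIDS) and a question about the young person's main activity at the time of the survey", and the SAP Design overview also lists prosocial identity among the baseline measures. The protocol's paragraph on the endline questionnaire instead groups PIDS with the scales left out at baseline. That paragraph stands alone against the rest, but the answer decides whether PIDS has a Y_i0.

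**The case against.** The strongest reply is that the plan already handles this. The SAP's LASSO model is meant to reduce unexplained variance, baseline SDQ scores are among its candidates, and they also enter the main model if imbalanced. So a reader who infers that the plan ignores these data goes too far. What remains is that the LASSO is a secondary specification, while the linear model is the main one and the adjusted-p decision rule is set out with it. Protocol Step 5 repeats the LASSO step for arrests and risk assessments, and Step 6, which covers these two outcomes, does not mention it. Its use here rests on the SAP's general wording.

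A second reply is that the gain may be trivial. That stands: different instruments about 20 weeks apart may correlate weakly, and at r = 0.2 power rises by only 2 points. The fall from 0.16 to 0.12 SD in the protocol's tables might be read as the expected gain. It concerns the same scale measured twice, so it is an optimistic guide for a proxy.

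Third, the protocol defines wellbeing, self-regulation and internalising behaviours as separate outcomes. Research question 3 groups them but does not call one a proxy for another. That is fair, and it is why r has to be assumed.

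Fourth, required covariates can lose participants. This also stands, as the last column of the table shows. It is limited because the SDQ comes from the same week-1 questionnaire that the primary model already needs.

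**Conclusion.** The point holds as a minor one about precision. The main models for SWEMWBS and TEIQUE-ASF pre-specify no prognostic covariate, although a related baseline score is available. The gain from using it runs from negligible (82% power at r = 0.2) to material (90% at r = 0.5, equivalent to about a third more participants). The documents cannot place it within that range. The power figures start from an externalising score and from sample assumptions the SAP has since revised, and they precede multiplicity adjustment.

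A reader might infer that the estimates for these outcomes are biased. The documents do not show that. Under the design's assumption that young people reach teams independently of training status, leaving out a prognostic covariate costs precision only. Young people are not themselves randomised, and the pilot found some allocators weighing risk and potential benefit, so imbalance below the significance threshold is a risk. Observed pilot characteristics were nevertheless well balanced.

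**What to change.** Add to the SAP, Secondary outcome analysis: *For outcomes with no baseline measure (SWEMWBS, TEIQUE-ASF self-regulation), the main model adjusts for the baseline continuous SDQ emotional and peer difficulties scores in place of Y_i0. Participants with a missing baseline SDQ are retained by simple imputation with a missing-data indicator.* Another method of retention would serve, provided complete-case loss does not cancel the gain.

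Keep the simple and LASSO models in Robustness checks. The simple model then becomes a genuine comparison for these two outcomes.

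Separately, reconcile the protocol's endline-questionnaire paragraph with its baseline-questionnaire paragraph and the SAP Design overview on PIDS. Only if PIDS was not in the baseline survey, use the baseline SDQ prosocial score for it in the same way.

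The cost is a short SAP addition and a few degrees of freedom. No new data are needed.

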#### Subgroup analyses

We will explore heterogeneous treatment effects by age, race/ethnicity, gender and practitioner risk assessment (when sample sizes allow this to be meaningfully done). Specifically, we will run separate models and test for statistically significant differences in effects across the following subgroups:

- Age 11-15 vs Age 16-18.
- White vs Non-White specifically, we would expect to compare those of Black backgrounds to those of White backgrounds and compare those of South Asian backgrounds to those of White backgrounds. This is on the basis that those from minoritised backgrounds may face more structural challenges that may impede the impact of Your Choice.
- Males vs Females.
- Medium vs High Risk based on baseline practitioner risk assessment (as per the baseline practitioner survey).

Note that the trial will not be powered to detect differences in impacts between any of these subgroups, so this analysis will be considered exploratory rather than definitive.

#### **Robustness checks**

We will run additional secondary specifications to test the robustness of the results to altering the covariates included in the model. In expectation, due to the randomisation of treatment, doing so should not change the point estimates of impact, but may change the confidence intervals.

Specifically, we will estimate the following specifications:

- A simple model, controlling only for the treatment assignment and strata fixed effect as covariates
- A model controlling for covariates selected using a post-double selection LASSO procedure. This procedure uses LASSO to select variables that are most predictive of the treatment status (i.e. that are most imbalanced between control and treatment groups) and another LASSO to select variables that are most predictive of the outcome variables (to decrease the unexplained variance). The procedure is therefore a data-driven procedure to select both sets of covariates and estimates the treatment impacts controlling for those.

Our main ITT parameters will be estimated using Ordinary Least Squares (i.e. linear probability models for binary outcomes, such as our primary outcome). When used for binary outcomes, the linear regression model is the least demanding model in terms of distributional assumptions and behaves well for probabilities away from the bounds 0 and 1. Its main drawback (of potentially generating out-of-sample prediction outside the 0-1 range) does not apply to this application as we are not using the model for predictions. The coefficients of the linear probability model can be directly interpreted as marginal effects. For binary outcomes, we will also estimate probit and/or logit models in robustness checks. These models behave better than the linear probability model at the tails. We will present marginal effects based on these models. We do not expect our findings to vary substantially with the choice of model.

